4.4. Safety Analyses

Safety analyses will be conducted using the Safety population and will be presented based on actual treatment received.

4.4.1. Study Drug Exposure

Study drug exposure will be tabulated by the number of doses received. The number and percentage of subjects will be reported by treatment group and overall.

Compliance will be measured by the following parameters: incorrect treatment received, unsuccessful EP, the location of the EP treatment, the size of EP array, and whether or not a guide was used.

Dosing information for each subject will be presented in a data listing.

Relevant Output

| Table 14.3.5.1 | Study Drug Exposure (Safety Population) |
|------------------|-----------------------------------------|
| Listing 16.2.5.1 | Study Drug Administration |
| Listing 16.2.5.2 | Electroporation Administration |
| Listing 16.2.5.3 | Electroporation Issue Reports |
| Listing 16.2.5.4 | Electroporation Guide Use |

4.4.2. Adverse Events

All AEs will be coded using the most current version of the MedDRA coding system and displayed in tables and data listings using system organ class (SOC) and preferred term.

Analyses of AEs will be performed for those events that are considered treatment-emergent, where treatment-emergent is defined per protocol as any AE with onset after the administration of study medication through the end of the study (i.e., study discharge).

An AESI is defined as an AE deemed related to VGX-3100 delivered with CELLECTRATM 2000 that requires expedited communication from the site to the Sponsor and meets any of the following criteria per the Toxicity Grade for Healthy Adults:

• Grade 3 or greater persistent administration site erythema, and/or induration recorded ≥2 hours immediately after study treatment;

- Grade 4 or greater persistent administration site pain, tenderness recorded ≥ 2 hours immediately after study treatment;
- Grade 3 or greater fever;
- Grade 3 or greater systemic symptoms, including generalized pruritus.

Separate summaries of AEs will be presented by treatment group and overall for events with an onset within the first 28, 14, and 7 days after injection and overall. The summary will include the number and percentage of subjects with any treatment-emergent AE (TEAE), with any TEAE assessed by the Investigator as related to treatment, with any AESI, with any TEAE by Common Terminology Criteria for Adverse Events (CTCAE v4.03) grade, with any SAE, with any pre-treatment AE, with any AE leading to discontinuation of treatment, and with any AE leading to death.

In these tabulations, each subject will contribute only once (i.e., the most related occurrence or the most intense occurrence) to each of the incidences in the analysis, regardless of the number of episodes. In addition to the number of subjects that experienced at least 1 of the events, the total number of events observed across subjects will also be reported.

Summary tables by SOC and preferred term will be produced for the following, presented by treatment group:

- All TEAEs
- All TEAEs by most recent injection
- All TEAEs by severity grade
- All TEAE assessed as at least possibly related to treatment by the Investigator (i.e., treatment-related)
- All TEAEs with onset within 7 days of an injection
- All TEAEs with onset within 7 days by severity grade
- All treatment-related TEAEs with onset within 7 days of an injection
- All TEAEs with onset within 14 days of an injection
- All TEAEs with onset within 14 days of an injection by severity grade
- All treatment-related TEAEs with onset within 14 days of an injection
- All TEAEs with onset within 28 days of an injection
- All TEAEs with onset within 28 days of an injection by severity grade
- All treatment-related TEAEs with onset within 28 days of an injection

For each tabulation, TEAEs are summarized by proportions of subjects; therefore, in any tabulation, a subject contributes only once to the count for a given TEAE (SOC or preferred term), irrespective of the number of episodes of a particular AE term reported. Injection site reactions are included in the TEAE summaries.

The frequency of subjects with preferred term events with onset within 7, 14, or 28 days separately will be summarized with percentages and exact Clopper-Pearson 95% CIs. All AEs occurring on-study will be listed in subject data listings. By-subject listings also will be

provided for the following: AEs leading to death, SAEs, AEs with severity \geq Grade 3, AEs leading to discontinuation of treatment, and AESIs.

| Table 14.3.1.1A | Overall Summary of Adverse Events (Safety Population) |
|-----------------|----------------------------------------------------------------------------------------------------------------------|
| Table 14.3.1.1B | Overall Summary of Treatment-Emergent Adverse Events with Onset within 7 Days of an Injection (Safety Population) |
| Table 14.3.1.1C | Overall Summary of Treatment-Emergent Adverse Events with Onset |
| | within 14 Days of an Injection (Safety Population) |
| Table 14.3.1.1D | Overall Summary of Treatment-Emergent Adverse Events with Onset |
| | within 28 Days of an Injection (Safety Population) |
| Table 14.3.1.2A | Treatment-Emergent Adverse Events by MedDRA System Organ Class |
| | and Preferred Term (Safety Population) |
| Table 14.3.1.2B | Treatment-Emergent Adverse Events with Onset within 7 Days of an |
| | Injection by MedDRA System Organ Class and Preferred Term (Safety |
| | Population) |
| Table 14.3.1.2C | Treatment-Emergent Adverse Events with Onset within 14 Days of an |
| | Injection by MedDRA System Organ Class and Preferred Term (Safety |
| | Population) |
| Table 14.3.1.2D | Treatment-Emergent Adverse Events with Onset within 28 Days of an |
| | Injection by MedDRA System Organ Class and Preferred Term (Safety |
| | Population) |
| Table 14.3.1.3A | Treatment-Emergent Adverse Events by Most Recent Injection, |
| | MedDRA System Organ Class and Preferred Term (Safety Population) |
| Table 14.3.1.3B | Treatment-Emergent Adverse Events with Onset within 7 Days of Each |
| | Injection by Most Recent Injection, MedDRA System Organ Class and |
| | Preferred Term (Safety Population) |
| Table 14.3.1.3C | Treatment-Emergent Adverse Events with Onset within 14 Days of Each |
| | Injection by Most Recent Injection, MedDRA System Organ Class and |
| | Preferred Term (Safety Population) |
| Table 14.3.1.3D | Treatment-Emergent Adverse Events with Onset within 28 Days of Each |
| | Injection by Most Recent Injection, MedDRA System Organ Class and |
| | Preferred Term (Safety Population) |
| Table 14.3.1.4A | Treatment-Emergent Adverse Events by MedDRA System Organ Class, |
| | Preferred Term, and Severity Grade (Safety Population) |
| Table 14.3.1.4B | Treatment-Emergent Adverse Events with Onset within 7 Days of an |
| | Injection by MedDRA System Organ Class, Preferred Term, and Severity |
| | Grade (Safety Population) |
| Table 14.3.1.4C | Treatment-Emergent Adverse Events with Onset within 14 Days of an |
| | Injection by MedDRA System Organ Class, Preferred Term, and Severity |
| | Grade (Safety Population) |

| Table 14.3.1.4D | Treatment-Emergent Adverse Events with Onset within 28 Days of an Injection by MedDRA System Organ Class, Preferred Term, and Severity Grade (Safety Population) |
|------------------|-------------------------------------------------------------------------------------------------------------------------------------------------------------------------|
| Table 14.3.1.5A | Treatment-Related Treatment-Emergent Adverse Events by MedDRA System Organ Class and Preferred Term (Safety Population) |
| Table 14.3.1.5B | Treatment-Related Adverse Events with Onset within 7 Days of an Injection by MedDRA System Organ Class and Preferred Term (Safety Population) |
| Table 14.3.1.5C | Treatment-Related Treatment-Emergent Adverse Events with Onset within 14 Days of an Injection by MedDRA System Organ Class and Preferred Term (Safety Population) |
| Table 14.3.1.5D | Treatment-Related Treatment-Emergent Adverse Events with Onset within 28 Days of an Injection by MedDRA System Organ Class and Preferred Term (Safety Population) |
| Table 14.3.2.1 | Listing of Adverse Events Leading to Death (Safety Population) |
| Table 14.3.2.2 | Listing of Serious Adverse Events (Safety Population) |
| Table 14.3.2.3 | Listing of Adverse Events with CTCAE Toxicity \geq Grade 3 (Safety Population) |
| Table 14.3.2.4 | Listing of Adverse Events Leading to Discontinuation of Treatment (Safety Population) |
| Table 14.3.2.5 | Listing of Adverse Events of Special Interest (Safety Population) |
| Listing 16.2.7.1 | Adverse Events by Subject, MedDRA Preferred Term, and Verbatim Term |
| Listing 16.2.7.2 | Adverse Events by MedDRA System Organ Class/Preferred Term and Subject |
| Listing 16.2.7.3 | Glossary of Adverse Events |

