Subjects in Subgroups C and D may receive a fifth and possibly a sixth dose at Week 52 and Week 78, respectively.

To assess quality of life and related impacts on subjects, PRO instruments will be provided and will include the Short Form Health Survey version 2 (SF-36v2TM), the EQ-5D-5L (EuroQol Research Foundation), WOMAN-PRO (WOMen with vulvAr Neoplasia) Clinical Trial Version 2.0, and 2 additional PRO questions assessing quality of life after surgery or biopsy.

The total duration of the study is up to 10 weeks for the screening period and up to100 weeks for the treatment and follow-up periods. The study duration is reduced to 78 weeks for subjects that have not already completed the Week 78 visit.

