3.10. Missing, Unused, and Spurious Data

When tabulating AE data, partial dates will be handled as follows in order to determine treatment emergence. If any of the day, month, or year is missing, the onset date will be set to the earliest date that is consistent with any non-missing date information, unless the non-missing date information is the same as study treatment start. In this case, in order to conservatively report the event as treatment-emergent, the onset date will be assumed to be the date of start of treatment. A completely missing onset date will be coded as the day of start of treatment.

A prior medication is defined as any medication that has a stop date before the start of the trial (prior to Dose #1 on Day 0). A concomitant medication is defined as any medication that has a stop date that is on or after the date of first dose of study drug. For prior and concomitant medications, partial start dates will not be imputed, as stop dates determine prior versus concomitant. Partial stop dates will be assumed to be the latest possible date consistent with the partial date.

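### The TEAE definition rests on onset alone, so a pre-treatment AE that worsens after the first dose on its original record is left out of the TEAE tables (minor)

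*SAP*

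**What the plan says.** Section 4.4.2 limits the AE analyses to treatment-emergent events and defines them in one sentence: "treatment-emergent is defined per protocol as any AE with onset after the administration of study medication through the end of the study". Section 3.10 gives the rule for incomplete dates, under which "partial dates will be handled as follows in order to determine treatment emergence". That rule works on the onset date and nothing else.

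Events that start before dosing are expected. The schedule in Section 1.2.4 marks AE collection at screening, and Section 1.2.1 says "The total duration of the study is up to 10 weeks for the screening period". The overall summary has a row for these events, named in the same list as the grade row: "with any TEAE by Common Terminology Criteria for Adverse Events (CTCAE v4.03) grade, with any SAE, with any pre-treatment AE". The relatedness row is also confined to TEAEs: "with any TEAE assessed by the Investigator as related to treatment".

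Outside the TEAE tables, Section 4.4.2 says "All AEs occurring on-study will be listed in subject data listings", and separate by-subject listings are "provided for the following: AEs leading to death, SAEs, AEs with severity" Grade 3 or above, events leading to discontinuation, and AESIs. Exact intervals are planned for one set of AE frequencies: "preferred term events with onset within 7, 14, or 28 days separately will be summarized with percentages and exact Clopper-Pearson 95% CIs".

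**The concern.** An AE that starts in screening at Grade 1 and rises to Grade 2 after a dose is a change on treatment. Under the stated rule its onset precedes the first dose, so it is not a TEAE whatever happens to its grade later. The system organ class and preferred term tables, the severity and relatedness tables, the most-recent-injection tables and the 7-, 14- and 28-day tables are all built on TEAEs, so it appears in none of them. In the overall summary it is counted in the pre-treatment row, which shows neither grade nor relatedness.

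The TEAE tables are the by-arm summary for the safety and tolerability objective in Section 1.1.3.2. At stake is a possible undercount of particular preferred terms, grades and related events in two small arms.

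**Working it through.** The SAP states no figure for this point, so there is none to reproduce. The check sets the rules side by side and then sizes one omitted subject.

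**Step 1: is there a worsening criterion anywhere?**
- Section 4.4.2: emergence depends on onset after study medication, up to study discharge.
- Section 3.10: a partial onset date is resolved towards treatment-emergent when it is compatible with the start of treatment. This helps where the date is ambiguous. It does nothing for an event known to have started before dosing.
- Section 1.2.5.3: says TEAEs are collected and names the 7-, 14- and 28-day windows. It adds no criterion.
- The rule in 4.4.2 that a subject contributes the most intense or most related occurrence selects among events already counted. It does not bring an excluded event in.
- Elsewhere in the SAP, worsening refers to the vulvar disease (Section 1.2.1 and the schedule footnotes), not to AEs.

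No section adds a worsening clause or says that a worsening opens a new record.

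**Step 2: where does a worsened pre-treatment AE on its original record appear?**

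| Output | Included? |
|---|---|
| TEAE tables: SOC/preferred term, severity, relatedness, most recent injection, 7/14/28 days | No |
| Overall summary: any TEAE, TEAE by grade, related TEAE | No |
| Overall summary: pre-treatment AE | Yes, without grade or relatedness |
| All-AE by-subject listings | Yes |
| SAE, Grade 3 or higher, AESI, discontinuation and death outputs | Only if it qualifies |

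The gap is therefore narrow. A non-serious worsening that stays below Grade 3, is not an AESI and does not stop treatment is visible only in the all-AE listings and the pre-treatment row.

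**Step 3: what is one omitted subject worth?** The inputs are the planned arm sizes in Section 1.2.1, 24 and 12, with 24 + 12 = 36 in total. The shift is 1/n, provided the subject has no other event counted in that row or term:
- Combination arm: 1/12 = 8.3 points.
- VGX-3100 alone: 1/24 = 4.2 points.
- All subjects: 1/36 = 2.8 points.

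The tables by SOC and preferred term are presented by treatment group, so the first two figures apply there. The overall summary is presented by treatment group and overall. Its arm columns also shift by 8.3 or 4.2 points, and 2.8 points applies only to its all-subject column.

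**Step 4: do the exact intervals move?** They are planned for the windowed preferred-term frequencies. They can change only if a date of worsening is recorded and falls in the window. For a term with no other case, the Clopper-Pearson 95% interval would go from 0/12 (0 to 26.5%) to 1/12 (0.2 to 38.5%), or from 0/24 (0 to 14.2%) to 1/24 (0.1 to 21.1%). The upper limits at zero events are 1 − 0.025^(1/n). Without a date of worsening these intervals stay as they are.

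**The case against.** The best case for the plan is that the definition is attributed to the protocol, which is not to hand, and that the handling of a worsening AE is a recording rule normally found there or in the CRF instructions. If those require a new AE with its own onset date, every worsening is already counted and the loss is zero. The SAP is also consistent: its definition, its date rule and its windowed tables all use onset. Injection site reactions cannot begin before the first injection, so that part of the tolerability data is untouched. With about 36 subjects the listings can be read in full, and no formal test of safety is planned.

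Most of this stands, and it sets the size of the point. It does not remove it. Section 4.4.2 writes out a complete rule rather than referring the matter elsewhere, and the SAP is where the tables are derived. Consistent use of onset does not repair the result for an event that worsens on its original record.

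A reader might infer more: that worsened screening events disappear from the report, or that the trial's TEAE rates are known to be too low. The SAP supports neither. The events stay in the listings and the pre-treatment row, and nothing in the SAP shows how often such events occur or that they are kept on one record.

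**Conclusion.** The point holds as a cheap improvement of minor weight. Read literally, the definition keeps a worsened pre-treatment AE on its original record out of all the TEAE tables and out of the TEAE-based rows of the overall summary.

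The SAP gives no rate, so only the effect per omitted subject can be stated: 8.3 or 4.2 points in the arm columns, and 2.8 points in the all-subject column of the overall summary. These figures assume the planned arm sizes as denominators and no other counted event for that subject in the same row or term. The total effect may be zero, depending on a recording rule that the SAP does not show. The efficacy conclusion is not affected.

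**What to change.** In Section 4.4.2, define a TEAE as any AE with onset after the first administration, or any pre-treatment AE that increases in severity after it. Then:

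- Assign events of the second kind to the most-recent-injection and 7/14/28-day tables by date of worsening, where that date is recorded.
- Where it is not, count them in the all-TEAE, severity and related tables, with a footnote that the windowed tables and their exact intervals do not include them.
- Note the departure from the protocol definition in Section 5, which at present reports no changes.

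If the recording rules already open a new AE at each worsening, one sentence in 4.4.2 saying so is enough, and Section 5 can stay as it is.

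The cost is a change of wording, slight extra derivation work and slightly higher reported TEAE rates. The clause can be applied only where the record captures a change in grade. Where the date of worsening is missing, the all-TEAE and windowed tables will count these events differently, which is why the footnote is needed.

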4.4.3. Laboratory Data

Clinical laboratory values will be expressed in International System (SI) units.

Clinical laboratory data will be collected at screening. All laboratory data will be provided in by-subject data listings, including hematology, clinical chemistry, creatinine phosphokinase, urinalysis, and pregnancy testing assessments.

| Listing 16.2.8.1 | Laboratory Results: Hematology |
|------------------|--------------------------------------------|
| Listing 16.2.8.2 | Laboratory Results: Serum Chemistry |
| Listing 16.2.8.3 | Laboratory Results: Urinalysis |
| Listing 16.2.8.4 | Laboratory Results: Creatine Phosphokinase |
| Listing 16.2.8.6 | Laboratory Results: Pregnancy |

4.4.4. Vital Signs and Physical Examination

The actual value and change from baseline to each on-study evaluation will be summarized for vital signs.

Physical examination results at each on-study evaluation will be summarized.

All physical examination findings and vital sign measurement will be presented in by-subject data listings.

Relevant Output

| Table 14.3.5.2 | Summary of Actual Value and Change from Baseline for Vital Signs by Scheduled Visit (Safety Population) |
|------------------|------------------------------------------------------------------------------------------------------------|
| Table 14.3.5.3 | Physical Examination Results by Scheduled Visit (Safety Population) |
| Listing 16.2.9.1 | Vital Signs |
| Listing 16.2.9.2 | Physical Examination Findings |

4.4.5. Electrocardiogram

A 12-lead electrocardiogram (ECG) will be performed at screening for all subjects and results will be provided in a by-subject data listing. The ECG results include ventricular rate and PR, QRS, QT, QTcB (calculated by the Bazett correction formula), ST Segment, and T-wave. QTcB will be calculated using the formula QT/\sqrt{RR} . The RR interval will be derived as 60 divided by the ventricular rate. All abnormal results and clinical significance will be flagged within listing.

Relevant Output

Listing 16.2.9.3 12-Lead Electrocardiogram Results

4.4.6. Prior and Concomitant Medications

Concomitant medications include all medications taken or medical procedures performed with a stop date that is on or after the date of first dose of study drug. The number and percentage of subjects with medications at anatomic therapeutic class (ATC) Class Level 3 and Preferred Term levels will be reported by treatment group and overall. Prior and concomitant medications will be presented separately.

The use of concomitant medications, including medications used for management of anxiety or pain due to the EP procedure, will be included in a by-subject data listings.

| Table 14.3.5.4 Table 14.3.5.5 | Prior Medications (Safety Population) Concomitant Medications (Safety Population) |
|----------------------------------|--------------------------------------------------------------------------------------|
| Listing 16.2.9.4A | Prior Medications |
| Listing 16.2.9.4B | Concomitant Medications |

7. STATISTICAL OUTPUT

7.1. List of Statistical Output to be Generated

The lists of statistical output are provided in separate documents for statistical tables and data listings.

7.2. Statistical Table Shells

Statistical table shells are provided in a separate document.

7.3. Data Listing Shells

Data listing shells are provided in a separate document.
